1.1 Study premise and specific research question

Premise: Pelvic girdle pain (PGP) in pregnancy is common with prevalence estimates of 45%.¹

It is defined as pain experienced between the posterior iliac crest and the gluteal fold, particularly in the region of the sacroiliac joint.² Pain may radiate in the posterior thigh and can also occur in conjunction with/or separately in the symphysis. In PGP, the endurance capacity for standing, walking and sitting is diminished. The diagnosis of PGP can be reached after exclusion of lumbar causes and must be reproducible by specific clinical tests. While various pain mechanisms including mechanical, hormonal, inflammatory, and neural have been proposed in the development of PGP, the etiology and pathogenesis is poorly understood. It is possible that musculoskeletal changes influenced by hormonal (Relaxin) elevation in pregnancy predispose pregnant women to acute musculoskeletal injury presenting clinically as PGP. An inflammatory response in other acute musculoskeletal injuries has been well described³ and may also occur in pregnancy related PGP particularly given the musculoskeletal vulnerability during this time. Though PGP is common in pregnancy, no study to date has investigated the efficacy of anti-inflammatory treatment in pregnancy related PGP in order to better establish the contribution of inflammation in the etiology of pregnancy related PGP.

Specific research question:

Can pregnancy related PGP be more effectively treated with the use of injectable anti-inflammatory medication plus lidocaine compared with a saline with lidocaine active comparator injection?

1.2 Specific study objectives

Primary question and response variable:

Does ultrasound guided posterior sacroiliac ligament corticosteroid injection combined with lidocaine provide superior pain relief in pregnant women with PGP in the second or third trimester compared with a saline with lidocaine active comparator injection as measured by the pain Numeric Rating Scale (NRS) (0-10)?

Primary outcome variables: Pain NRS (0-10) (anchors: 0 = none, 10 = worst imaginable)

Secondary questions and response variable:

Does posterior sacroiliac ligament corticosteroid injection combined with lidocaine in pregnant women with PGP in the second/third trimester result in less disability and improved physical examination as compared with a saline with lidocaine active comparator injection?

Secondary outcome variables: Oswestry Disability Index (ODI), Pelvic Girdle Questionnaire (PGQ) and physical examination testing including the Patrick's Faber test, the Posterior Pelvic Pain Provocation test (PPPP or P4), long dorsal ligament (LDL) palpation, pubic symphysis palpation, the modified Trendelenburg test and the Active Straight leg raise (ASLR) test.

1.3 Summary of the study design

Study design: Randomized double blinded controlled trial.

Power calculation: Sample size (total and in each treatment group): A minimum of 50 participants, 25 in each treatment group would be sufficient to detect a treatment effect of a 2 point change in NRS at the 4 and 8 week follow-up period with 80% power at a 5% significance level (two tailed). 5 patients will be added to each group to account for a 10% loss to follow-up rate.

Population: Clinic-based patients seen at the at the Loyola University Medical Center, Gottlieb Hospital Obstetrics Clinics or patients referred from Chicagoland area hospitals or physical therapy practices

Intervention Group: Ultrasound guided posterior sacroiliac ligament corticosteroid plus lidocaine injection

Control Group: A saline with lidocaine active comparator injection

Follow-up: Conducted at 7 days, 4 weeks, 8 weeks and 6 weeks postpartum after intervention

Primary Outcome measure: Pain Numeric Rating Scale (NRS) (0-10)

Secondary Outcome measures: ODI, PDQ, and physical examination testing

2. Rationale

Pelvic girdle pain (PGP) often described by patients as “sciatica” is an important problem in pregnancy that can lead to significant functional disability⁴, postpartum chronic pelvic pain⁵, depression⁶ and adversely affect future child-bearing decision making⁷. Current treatment utilizes physical therapy (PT) with stabilizing exercises and this is supported by the literature^{8,9}. Clinically, however, there is often a group of severe pain patients (often those with pelvic girdle syndrome, i.e. bilateral sacroiliac joint and pubic symphysis pain) that do not respond to physical therapy alone and have the poorest prognosis^{10,11}. These are the same patients who typically go on to persistent postpartum chronic PGP. Optimal pain relieving treatment in pregnancy could possibly prevent chronic PGP postpartum and the significant long-term disability associated with it.

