Patients will be approached in their second or third trimester regarding the study in the Obstetrics or Rehabilitation clinics if they have PGP. They will be given a flyer regarding the study. If interested in participating, they will either proceed to study visit 1 (baseline), if time permits, or set up a separate time for study visit 1 to take place. Patients will be consented and evaluated for eligibility at this baseline visit. Eligible patient will be randomized to either the control or intervention groups at study visit 1. They will receive the injected medication at study visit 1. This study will require study visits total, study visit 1 will be at the time of randomization,

study visit 2 will be 4 weeks after injection, study Visit 3 will be at 8 weeks after start of intervention/after injection. and study visit 4 will be 6 weeks post-delivery. There will be one follow-up phone call between visit 1 and 2 on day 7 following intervention to inquire about any medication side effects or adverse events. Study duration is 8 weeks per patient, with an expected two year total recruitment and data collection time period. At study visit 1, patients will be randomized to receive the intervention medication or active comparator and undergo a physical examination of the external musculoskeletal pelvis and will complete the NRS for 'worst pain' and 'mean pain' during the latest 48 hours, a pain diagram, a personal health information questionnaire regarding their pregnancy, past medical history, activity level and restrictions. Disability as measured by the Pelvic Girdle Questionnaire (PGQ) and Oswestry Disability Index (ODI), Health-Related Quality of Life (HRQL) measured by the Wellbeing NRS and work ability will be measured with one question from Workability Index i.e. "Current work ability compared with the lifetime best".

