Those randomized to the will receive either 40mg of a non-fluorinated injectable glucocorticoid, methylprednisolone acetate (1cc) combined with 1cc of 1% Lidocaine or 1cc f1% Lidocaine plus 1cc of normal saline. The injection will be performed unilaterally if pain is single sided or bilaterally if the pain is in both sacroiliac joint regions The injection will be ultrasound guided and performed by the PI [name] who is trained in musculoskeletal ultrasound and ligamentous injections as a specialist in physical medicine and rehabilitation. [name] and the participant will both be blinded to the type of injectate used. Study visits 2 and 3 will include the same questionnaires and physical examination and will document any change in the pregnancy status. Study visit 4 will occur 6 weeks post-delivery and will include the same questionnaires and physical examination to determine if any chronic pain remains. Patients will be allowed to utilize acetaminophen as needed and the amount utilized in each intervention arm will be recorded. Total study visit time is expected to be 60 minutes for study visit 1 and 30 minutes for visits 2-4. Standard physical examination maneuvers validated for the assessment Protocol Version 4 – 03-06-2015

of pregnancy related PGP will be performed by the PI [name] and include pelvic pain provocation tests and functional stability testing. It will be noted with each maneuver whether the test was positive or negative. They will include:

a. *Patrick's Faber test*: With the patient in supine, the patient's leg is flexed, abducted and externally rotated so that the heel rests on the opposite kneecap. This test is positive with production of pain in the sacroiliac joint.

b. *Posterior Pelvic Pain Provocation (P4) test*: with the patient supine, the femur is flexed to be perpendicular with the table at 90 degrees and the knee is flexed at 90 degrees. A gentle force is applied to the femur in the direction of the examination table. The test is positive when the patient experiences pain in the gluteal region of that leg.

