3.6 Schedule of events

(Refer to Appendix I for schedule of events, Appendix II for study timeline and to Appendix IV for study forms, attached pdfs)

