3.8 Analysis

Data will be analyzed using descriptive univariate statistics with STATA 11.0. In this population, there is evidence from current literature that pain and disability may not be normally distributed. If this is the case, the primary and secondary outcomes, pain and disability respectively, will be presented as median values and interquartile ranges. Comparisons between the intervention groups at follow-up will be performed using the Mann Whitney U test and change within groups from baseline to follow-up will be examined using the Wilcoxon signed-rank test. If data are sufficiently normally distributed and differences are found, multivariate analyses will be conducted. This will determine the need to control for group differences based on location of pain, history of low back pain or pelvic girdle pain, age, educational level, parity, and time from pain onset. Additional secondary analyses will examine the impact of the treatment group assignment on physical examination tests using chi-square test of proportions.

4. Risks and Benefits

The excellent overall safety and efficacy record of injectable corticosteroids is well established²⁶. A prospective evaluation of intraarticular and periarticular injections with methylprednisolone found a very low rate of complications²⁷. Systemic effects of injectable corticosteroids are influenced by the agent used, dose, frequency and number of sites injected. Osteoporosis is found only with use of systemic/oral steroids and myopathy more commonly documented with oral fluorinated steroid use has not been reported with intraarticular injections. The ability of intraarticular injections to suppress the hypothalamic-pituitary-adrenal (HPA) axis

Protocol Version 4 – 03-06-2015

is well documented²⁸ but has not been described with extraarticular or ligamentous injections. A corticosteroid induced increase in glucose synthesis is not seen in soft-tissue injections of methylprednisolone acetate²⁹.

Fetal Risk and Benefit

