Appendix II: Sample Size Calculations

Sample size was determined under the assumption that a difference of 2 on NRS would have clinical relevance. This was based on the previous work of Elden¹⁴ in an RCT for acupuncture compared with sham for PGP in pregnancy. The 2 point difference on the NRS has also been used in other gynecologic RCTs in the measurement of pain.³³ The standard deviation of 25 mm was derived from the prior work of Bastiaenen¹⁶ in an RCT comparing a specific educational physical therapy program to usual care in postpartum PGP. No standard deviations were available in the Elden paper or in any other literature on this topic. For the primary outcome of patient pain ratings (0-10 NRS) after 4 weeks of physical therapy with or without methylprednisolone, a sample size of 50 (25 in each group) will give the study 80% power to identify a 2 point difference on the NRS (with [alpha] of .05). The 4 week follow-up time period is used because the clinical effect of the study medication is expected within the 4 weeks. An additional 5 participants in each group is added to account for a loss to follow-up of 10% which calculates to then 30 per treatment group. Power analyses were performed by using STATA

11.0. The basic formula for calculation is $\Delta/\sigma = 3.96/\sqrt{n}$, with Δ = effect size, σ = the standard deviation and n = number of patients needed.

Sensitivity analysis

Expected change in NRS (Effect size)	N if Power 80%	N if Power 90%
1	198 (99 per group)	264 (132 per group)
1.5	88 (44 per group)	118 (59 per group)
2	50 (25 per group)	66 (33 per group)
3	22 (11 per group)	30 (15 per group)

References:

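### The primary endpoint is not uniquely defined: two NRS pain scores are collected and neither is named primary, and the power statement in 1.3 covers 4 and 8 weeks while Appendix II fixes 4 weeks

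*Combined protocol and SAP*

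**What the plan says.** **Which score.** Section 1.2 has "Primary outcome variables: Pain NRS (0-10" and section 1.3 has "Primary Outcome measure: Pain Numeric Rating Scale (NRS) (0-10"; neither adds a qualifier. The visit 1 description in section 3 (Protocol) shows that there are two such scores: patients "will complete the NRS for 'worst pain' and 'mean pain' during the latest 48 hours". The same section adds that "Study visits 2 and 3 will include the same questionnaires and physical examination", and says the same of the postpartum visit. The entry rule in 3.1 uses an average NRS of at least 5, but applies to eligibility only.

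**Which time.** Section 1.3 describes 25 per group as "sufficient to detect a treatment effect of a 2 point change in NRS at the 4 and 8 week follow-up period with 80% power". Appendix II (Sample Size Calculations) instead reads "For the primary outcome of patient pain ratings (0-10 NRS) after 4 weeks of physical therapy with or without methylprednisolone" and justifies 4 weeks by when the drug effect is expected. Section 3.5.4 gives the 8-week visit a different purpose, durability of effect, and the postpartum visit another, residual chronic pain.

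**Which test.** For non-normal data, 3.8 states "Comparisons between the intervention groups at follow-up will be performed using the Mann Whitney U test". It gives no score, visit, hierarchy or multiplicity rule.

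**A limit on what can be read.** Section 3.6 refers to "Appendix IV for study forms, attached pdfs", and those forms are not part of the text available. That both scores recur at follow-up is therefore inferred from the statement that the questionnaires are the same.

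**The concern.** An analyst holding only this plan could not tell which variable to test for the primary hypothesis. Two scores at 4 and 8 weeks make four between-group comparisons, each of which fits the description of a pain NRS at follow-up. If the choice is left open until the data are unblinded, the primary result can be selected, and later wording cannot repair that.

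The timing discrepancy is the lesser part. Appendix II and 3.5.4 already point to 4 weeks, but the power sentence in 1.3 can be read as covering either time or as requiring both, and 3.8 does not settle it. The 5% level and 80% power are stated for a primary test that the plan does not pin down.

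**Working it through.** **Inputs.** Two-sided 5% and 80% power (3.7), difference 2 points, SD 25 mm (Appendix II), 1:1 allocation (3.5.2), 30 enrolled per group with 10% loss (1.3, Appendix II). Assumptions: 25 mm is read as 2.5 NRS points; the documents give no correlations between scores or visits, so ranges are used.

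**1. The plan's own figure.** n per group = 2(z₀.₉₇₅ + z₀.₈₀)²(σ/Δ)² = 2 × (1.960 + 0.842)² × (2.5/2)² = 24.5, so 25. Appendix II's formula agrees: (3.96 × 2.5/2)² = 24.5. The stated 25 per group reproduces, for one score at one time.

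**2. Power of one named comparison.** Power ≈ Φ(0.8√(n/2) − 1.960), where 0.8 = 2/2.5. For 25 per group this is Φ(2.828 − 1.960) = Φ(0.868) = 80.7%. For 27 evaluable (30 × 0.9) it is Φ(2.939 − 1.960) = Φ(0.979) = 83.6%.

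| Evaluable per group | Normal approx. | t-test | Mann-Whitney (simulated, normal data) |
|---|---|---|---|
| 25 | 80.7% | 79.1% | about 77% |
| 27 | 83.6% | 82.2% | about 80% |

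**3. If either score could count at 4 weeks.** Error = 1 − P(|Z₁| ≤ 1.96 and |Z₂| ≤ 1.96), with (Z₁, Z₂) bivariate normal with correlation r:

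| r between scores | 0.5 | 0.6 | 0.7 | 0.8 | 0.9 |
|---|---|---|---|---|---|
| Type I error | 9.1% | 8.8% | 8.3% | 7.8% | 7.0% |

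Simulated Mann-Whitney tests on whole-number 0-10 scores at 25 per group give 8.9%, 8.4% and 7.2% at underlying correlations of 0.5, 0.7 and 0.9, so the result does not depend on the normal approximation.

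**4. If either score at either 4 or 8 weeks could count.** Four tests, with the correlation matrix formed as the product of a score correlation and a visit correlation, 2,000,000 draws:

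| Score r | Visit r 0.3 | Visit r 0.5 | Visit r 0.7 |
|---|---|---|---|
| 0.5 | 16.9% | 16.1% | 14.8% |
| 0.7 | 15.6% | 14.9% | 13.7% |
| 0.9 | 13.3% | 12.6% | 11.6% |

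**5. If one score must succeed at both 4 and 8 weeks.** The error rate is then at most 5%. With a true 2-point effect at both times, joint power = Φ₂(0.868, 0.868; r) at 25 per group, and Φ₂(0.979, 0.979; r) at 27:

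| Visit r | 0.3 | 0.5 | 0.7 | 0.9 |
|---|---|---|---|---|
| 25 per group | 67.7% | 69.7% | 72.2% | 75.9% |
| 27 per group | 72.0% | 73.8% | 76.0% | 79.2% |

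Every entry is below the 80% stated in 1.3.

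**The case against.** The strongest reply is that the plan never says any one of several tests may count as success. That stands. A reader might infer from the missing rule that this trial runs at 7-17% type I error. The documents do not support that, because each such figure needs a decision rule that no section adopts. What they support is that nothing in the plan rules such a choice out.

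Second, the time is largely settled: Appendix II names 4 weeks with a reason, and 3.5.4 gives the later visits other purposes. That also stands. Section 3.8 is silent on time rather than in conflict with Appendix II; only 1.3 departs from it. On its own, the time part is a consistency edit.

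Third, the average-NRS entry rule suggests that mean pain was intended. It is a fair hint, but nothing carries it from eligibility to the outcome.

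Fourth, the unseen forms might help. They could confirm whether both scores are repeated, but sections 1.2, 1.3, 3.8 and Appendix II are where the primary variable would be designated, and none does so.

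Finally, worst and mean pain are probably highly correlated. Even at 0.9 the error under an either-counts rule is 7.0%.

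**Conclusion.** The point holds in this form: the primary endpoint is not uniquely defined, mainly because the score is undesignated and secondarily because the time in 1.3 differs from Appendix II. Overall control at 5% is not assured. If either score could count at 4 weeks, the error is about 7.0-9.1% (score correlation 0.9 to 0.5). If either time could count as well, it is about 12-17% (visit correlation 0.7 to 0.3). If both times must be significant, the error is not inflated, but joint power is about 68-76% at 25 per group (visit correlation 0.3 to 0.9). All correlations are assumptions, and recurrence of both scores at follow-up is inferred.

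A reader might also conclude that the sample size is wrong. It is not: 25 per group is correct for one comparison at one time under the normal approximation. The t-test and Mann-Whitney fall slightly short of 80% at 25, and reach about 80% or more at the 27 expected to be evaluable. Which test 3.8 should use is a separate question.

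**What to change.** Before unblinding, name one NRS score at 4 weeks after injection as the single primary endpoint, in identical words in 1.2, 1.3, 3.8 and Appendix II. The 48-hour mean score matches the entry rule in 3.1; the worst-pain score is equally acceptable if prespecified. Identify the endpoint by time rather than visit number, because section 3 calls the 4-week assessment visit 2 while Appendix I numbers it 3.

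In the power statement of 1.3, delete the reference to 8 weeks. In 3.8, replace the general reference to follow-up with the named score and time for the primary test. Label the other score, and the 8-week and postpartum comparisons, as secondary, reported with confidence intervals and without any claim of primary success.

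The cost is wording in four places. Sample size stays at 25 evaluable and 30 enrolled per group, and no visits change. The small downside is that an effect seen only at 8 weeks, or only on the other score, could not be claimed as success on the primary endpoint.

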2.1 Research to date

Randomized clinical trials on exercise/physical therapy interventions^{12,13}, acupuncture¹⁴ and an educational intervention^{15,16} have been performed in the study of PGP during pregnancy. There are currently no randomized clinical trials, however, evaluating the use of pain medications or corticosteroids for PGP in pregnancy. Torstensson et al performed a randomized double blind controlled trial evaluating the use of intravaginal corticosteroid injection at the ischiadic spine in postpartum women with persistent sacral pain. Slow release triamcinolone and lidocaine provided superior pain relief compared with saline and lidocaine alone.¹⁷ Musculoskeletal ultrasound (US) has been widely utilized in other musculoskeletal joint disorders to diagnose pathology¹⁸ and recently to identify the posterior sacroiliac joint ligamentous structures¹⁹. It has also been used to evaluate the sacroiliac joint in the non-

pregnant state for the purpose of diagnostic (anesthetic) joint injection with good success²⁰. US is already routinely being performed for obstetrical use during pregnancy and is considered safe in pregnancy due to its lack of radiation exposure²¹.

Glucocorticoids constitute one of the most frequently prescribed medications during pregnancy, used commonly in preeclampsia and for maternal inflammatory, dermatologic, and autoimmune disorders. Antenatal glucocorticoids are used for a multitude of reasons in pregnancy. Examples of use are asthma refractory to inhalant therapy (*National Asthma Education and Prevention Program: Full Report of the Expert Panel: Managing asthma during pregnancy: Recommendations for pharmacologic treatment – 2004 update. NHLBI, NIH publication no. 005-3279I*), autoimmune disorders^{22,23} and for acceleration of fetal lung maturity for women at risk of preterm birth²⁴.

Although fluorinated glucocorticoids are known to cross the placenta readily, the majority of prednisone and methylprednisolone (non-fluorinated glucocorticoids) are inactivated in the placenta and do not reach the fetus in significant concentrations. Both of the latter are Category C agents in that animal studies show no risk but no definitive studies in humans have been done, and may be safely used as anti-inflammatory/immunosuppressive agents if indicated in pregnancy²⁵.

3. Protocol (See Appendix II and III)

Patients will be approached in their second or third trimester regarding the study in the Obstetrics or Rehabilitation clinics if they have PGP. They will be given a flyer regarding the study. If interested in participating, they will either proceed to study visit 1 (baseline), if time permits, or set up a separate time for study visit 1 to take place. Patients will be consented and evaluated for eligibility at this baseline visit. Eligible patient will be randomized to either the control or intervention groups at study visit 1. They will receive the injected medication at study visit 1. This study will require study visits total, study visit 1 will be at the time of randomization,

study visit 2 will be 4 weeks after injection, study Visit 3 will be at 8 weeks after start of intervention/after injection. and study visit 4 will be 6 weeks post-delivery. There will be one follow-up phone call between visit 1 and 2 on day 7 following intervention to inquire about any medication side effects or adverse events. Study duration is 8 weeks per patient, with an expected two year total recruitment and data collection time period. At study visit 1, patients will be randomized to receive the intervention medication or active comparator and undergo a physical examination of the external musculoskeletal pelvis and will complete the NRS for 'worst pain' and 'mean pain' during the latest 48 hours, a pain diagram, a personal health information questionnaire regarding their pregnancy, past medical history, activity level and restrictions. Disability as measured by the Pelvic Girdle Questionnaire (PGQ) and Oswestry Disability Index (ODI), Health-Related Quality of Life (HRQL) measured by the Wellbeing NRS and work ability will be measured with one question from Workability Index i.e. "Current work ability compared with the lifetime best".

Those randomized to the will receive either 40mg of a non-fluorinated injectable glucocorticoid, methylprednisolone acetate (1cc) combined with 1cc of 1% Lidocaine or 1cc f1% Lidocaine plus 1cc of normal saline. The injection will be performed unilaterally if pain is single sided or bilaterally if the pain is in both sacroiliac joint regions The injection will be ultrasound guided and performed by the PI [name] who is trained in musculoskeletal ultrasound and ligamentous injections as a specialist in physical medicine and rehabilitation. [name] and the participant will both be blinded to the type of injectate used. Study visits 2 and 3 will include the same questionnaires and physical examination and will document any change in the pregnancy status. Study visit 4 will occur 6 weeks post-delivery and will include the same questionnaires and physical examination to determine if any chronic pain remains. Patients will be allowed to utilize acetaminophen as needed and the amount utilized in each intervention arm will be recorded. Total study visit time is expected to be 60 minutes for study visit 1 and 30 minutes for visits 2-4. Standard physical examination maneuvers validated for the assessment Protocol Version 4 – 03-06-2015

of pregnancy related PGP will be performed by the PI [name] and include pelvic pain provocation tests and functional stability testing. It will be noted with each maneuver whether the test was positive or negative. They will include:

a. *Patrick's Faber test*: With the patient in supine, the patient's leg is flexed, abducted and externally rotated so that the heel rests on the opposite kneecap. This test is positive with production of pain in the sacroiliac joint.

b. *Posterior Pelvic Pain Provocation (P4) test*: with the patient supine, the femur is flexed to be perpendicular with the table at 90 degrees and the knee is flexed at 90 degrees. A gentle force is applied to the femur in the direction of the examination table. The test is positive when the patient experiences pain in the gluteal region of that leg.

c. *Long Dorsal Sacroiliac Ligament (LDL) palpation test*: The subject lies on her side with slight flexion in both hip and knee joints. Specifically, the LDL is palpated directly caudomedially from the posterior iliac spine to the lateral dorsal border of the sacrum if palpation causes pain that persists five seconds after removal of the examiner's hand, it is recorded as pain. If the pain disappears within five seconds, it is recorded as tenderness. When the identical pain is felt directly in the vicinity, but outside the borders of the ligament, the test is not deemed as positive.

d. *Pubic Symphysis palpation test*: Examiners will palpate the subject's pubic symphysis joint while the patient is lying supine for tenderness. If palpation causes pain that persists five seconds after removal of the examiner's hand, it is recorded as pain. If the pain disappears within five seconds, it is recorded as tenderness.

e. *Modified Trendelenburg's test*: The standing woman stands on one leg and flexes the other at 90° (hip and knee). The test is considered positive if pain is experienced in the symphysis.

f. *Active Straight Leg Raise (ASLR) test*: performed with the patient supine with straight legs extended on the table 20 cm apart. The patient raises each leg one at a time 20 cm above the table without bending the knee. A) The test is positive when the patient describes a heaviness or difficulty in performing the task. B) In the second part of the maneuver, posterior

compression is applied and the patient is then asked to actively perform a straight leg raise. If there is greater ease in lifting the leg this is considered a positive test. The patient will be asked to score impairment (scoring inadequacy to raise the legs but not pain) on a 6-point scale: not difficult at all = 0, minimally difficult = 1, somewhat difficult = 2, fairly difficult = 3, very difficult = 4, unable to do = 5, the scores of both sides will be added so that the summed score can range from 0-10. Impairment is considered severe if the summed bilateral score is at least 4.

Personal Health Information to be collected The personal health information (PHI) items that will be collected during pregnancy will include: name, phone number; date of birth; BMI; height; age; race; education level; income level; number of previous pregnancies; number of previous deliveries; types of previous deliveries, past abdominal surgeries if any, current medications; history of other pain diagnoses, history of depression; history of neurological disease; history of anxiety; history of sexual abuse; previous low back injury; previous low back or pelvic pain; history of smoking; history of infertility; history of urinary or fecal incontinence; history of interstitial cystitis; history of arthritic conditions (osteoarthritis, rheumatoid arthritis, lupus); body parts affected by arthritic conditions; diabetes (Type I, Type II, gestational); gestational week of current pregnancy; due date of current pregnancy; number of babies expected; trimester/gestational week of onset of low back and/or pelvic pain (if applicable); current pregnancy complications; occurrence of miscarriage; activity and exercise types and levels during pregnancy; activity level restrictions; and duration for any previous physical therapy; previous home exercise program; and physical therapy descriptions and reasons for initiating therapy after enrollment in the study. Social history including marital status, support at home, and type of occupation will be documented.

3.1 Eligibility criteria:

- English speaking pregnant women presenting in their second or third trimester with posterior PGP. Trimester will be determined from date of last menses or ultrasound date.

- Women who have failed physical therapy for pain management (physical therapy, chiropractic management, aquatic therapy)
- Pain NRS on average of greater than or equal to 5/10 at Visit 1
- Pain must be between the upper level of the iliac crests and the gluteal folds in conjunction with or separately from pain in the pubic symphysis and influenced by position and locomotion
- 2/4 positive physical examination tests on the symptomatic side including the P4 test, the LDL test, pubic symphysis palpation and the ASLR

3.2 Exclusion criteria:

- Non-English speaking pregnant women <21 or >50 years old
- Women presenting with PGP in the first trimester (<13 weeks gestation)
- Women with pubic symphysis (anterior) pain alone
- Women who have not yet received some form of physical therapy for their pain
- Pain above the upper level of the iliac crest
- History of lumbar or pelvic fracture, neoplasm, inflammatory disease, active urogenital infection or active gastrointestinal illness, current physical therapy or other therapies for PGP, or previous surgery of the lumbar spine, pelvic girdle, hip joint or femur
- History or signs of radiculopathy or other systemic neurologic disease
- Women with diabetes or gestational diabetes

